# Table 2. Statistical power expected with proposed sample size of 1980 at different malaria

prevalence and different sensitivity of hsRDT (assumed sensitivity of 20% or 50% and specificity 95%)

| Prevalence
by usPCR | Sensitivity
of hsRDT | Specificity
of hsRDT | Estimated
prevalence
by hsRDT | Power | Sensitivity
of hsRDT | Specificity
of hsRDT | Estimated
prevalence
by hsRDT | Power |
|------------------------|-------------------------|-------------------------|-------------------------------------|-------|-------------------------|-------------------------|-------------------------------------|-------|
| 0.02                   | 0.2                     | 0.95                    | 0.009                               | 0.053 | 0.5                     | 0.95                    | 0.059                               | >0.99 |
| 0.03                   | 0.2                     | 0.95                    | 0.011                               | 0.055 | 0.5                     | 0.95                    | 0.064                               | >0.99 |
| 0.06                   | 0.2                     | 0.95                    | 0.017                               | 0.059 | 0.5                     | 0.95                    | 0.077                               | 0.79  |
| 0.12                   | 0.2                     | 0.95                    | 0.029                               | 0.068 | 0.5                     | 0.95                    | 0.104                               | 0.61  |

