# 7. Statistical consideration and Data Management

## 7.1. Power calculation with available sample size

The primary limitation is the size of population that needs to be screened since malaria burden may be low in the study sites, and associated financial costs and logistical difficulties.

The primary endpoint of this proposed study is the prevalence of secondary malaria cases identified by hsRDT in comparison with usPCR prevalence. Based on our current data on prevalence of *P. falcipaum* in 2016, and logistical and financial considerations, the recruitment of 50 index cases is feasible in a given study period. This will give us a total of 1980 individuals for testing of secondary cases in ACD, assuming the average household member of 4.5, 11 households for each index case (counting the household of the index case) and a refusal rate of 20% (4.5 persons/HH x 11 HH x 50 index cases x 0.80=1980).

We conservatively estimate that hsRDT will detect 20% of usPCR+ *P. falciparum* infections (i.e., sensitivity of hsRDT=0.2 using usPCR as gold standard). We expect very few recently treated individuals to be enrolled in the study, so that hsRDT should only rarely give a positive result when usPCR does not. Hence we assume that the specificity of hsRDT is 0.995. Table 1 shows estimated statistical power that can be achieved with the proposed sample size of 1980 for comparing the prevalence by hsRDT and the prevalence by usPCR, at different malaria prevalence by usPCR and different sensitivity of hsRDT, using a two-sided McNemar test with a Type I error of 5%. (PASS version 11. NCSS, LLC. Kaysville, Utah, USA)

As shown in Table 1, if the sensitivity of hsRDT is 0.2 and the specificity of hsRDT is 0.995, a sample size of 1980 subjects achieves at least 92% power to detect the difference in prevalence between hsRDT and usPCR when the malaria prevalence is 2% or higher. If the sensitivity of hsRDT is 0.5 (see the last four columns of Table 1), a sample size of 1980 subjects achieves at least 86% power when the malaria prevalence is 3% or higher. If the prevalence of malaria is higher, the performance of hsRDT will be better with a higher sensitivity and positive predictive value.

 Table 1. Statistical power expected with proposed sample size of 1980 at different malaria

| prevalence and different sensitivity of hsRDT (assumed sensitivity of 20% or 50% and |
|--|
| specificity 99.5%)   |

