| Prevalence
by usPCR | Sensitivity
of hsRDT | Specificity of hsRDT | Estimated
prevalence
by hsRDT | Power | Sensitivity
of hsRDT | Specificity
of hsRDT | Estimated
prevalence
by hsRDT | Power |
|------------------------|-------------------------|----------------------|-------------------------------------|-------|-------------------------|-------------------------|-------------------------------------|-------|
| 0.02                   | 0.2                     | 0.995                | 0.009                               | 0.92  | 0.5                     | 0.995                   | 0.015                               | 0.45  |
| 0.03                   | 0.2                     | 0.995                | 0.011                               | >0.99 | 0.5                     | 0.995                   | 0.020                               | 0.86  |
| 0.06                   | 0.2                     | 0.995                | 0.017                               | >0.99 | 0.5                     | 0.995                   | 0.035                               | >0.99 |
| 0.12                   | 0.2                     | 0.995                | 0.029                               | >0.99 | 0.5                     | 0.995                   | 0.065                               | >0.99 |

Table 2 below shows changes in the power of the study, if the specificity of hsRDT is 0.95 (increased false positive by hsRDT), while the sensitivity of hsRDT and baseline true prevalence remain the same.

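### Table 2, sensitivity-0.2 half: the power column holds hsRDT prevalences and the prevalence column repeats Table 1, so no power is given for specificity 0.95

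*Combined protocol and SAP*

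**What the plan says.** Section 7.1 of the combined protocol and SAP powers the study for "comparing the prevalence by hsRDT and the prevalence by usPCR", "using a two-sided McNemar test with a Type I error of 5"%, with 1980 people tested around 50 index cases. The base case is "sensitivity of hsRDT=0.2 using usPCR as gold standard", and for false positives: "Hence we assume that the specificity of hsRDT is 0.995". Table 1 gives the results for that specificity.

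The plan then varies specificity alone: "Table 2 below shows changes in the power of the study, if the specificity of hsRDT is 0.95", with sensitivity and usPCR prevalence kept as in Table 1. The caption of Table 2 confirms the scenario: "prevalence and different sensitivity of hsRDT (assumed sensitivity of 20% or 50% and specificity 95"%.

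For sensitivity 0.2, at usPCR prevalences of 0.02, 0.03, 0.06 and 0.12, Table 2 prints:

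- estimated hsRDT prevalence 0.009, 0.011, 0.017, 0.029
- power 0.053, 0.055, 0.059, 0.068

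**The concern.** Two features of the left half of Table 2 do not fit its stated scenario. The hsRDT prevalences are the same in all four rows as those in the left half of Table 1, although specificity has dropped from 0.995 to 0.95. The powers also rise slowly and almost linearly with prevalence, whereas power for a difference between two paired proportions should depend on how far apart they are.

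Table 2 is the plan's only examination of what false positives do to the primary comparison. As printed, it tells the reader that at specificity 0.95 the study has 5–7% power at every prevalence, and that hsRDT would call at most 2.9% of people positive. If both columns are wrong, the reader misses two things. At low prevalence hsRDT would find more positives than PCR. At one particular prevalence its false positives and false negatives cancel, so the comparison cannot tell a poor test from PCR.

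**Working it through.** **Inputs (Section 7.1).** n = 1980 paired subjects; two-sided McNemar test, alpha 0.05; sensitivity (Se) 0.2 or 0.5; specificity (Sp) 0.995 in Table 1 and 0.95 in Table 2; usPCR prevalence p = 0.02, 0.03, 0.06, 0.12.

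**Formulas.**

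- PCR-positive, hsRDT-negative: p10 = p(1 − Se)
- PCR-negative, hsRDT-positive: p01 = (1 − p)(1 − Sp)
- hsRDT prevalence = p·Se + (1 − p)(1 − Sp)
- With d = |p10 − p01| and s = p10 + p01, power = Φ[(d√n − 1.96√s)/√(s − d²)] + Φ[(−d√n − 1.96√s)/√(s − d²)]

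**Step 1: does the method reproduce the plan's other figures?**

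| Scenario | Row (p) | Printed power | Normal approximation |
|---|---|---|---|
| Table 1, Se 0.2 | 0.02 | 0.92 | 0.93 |
| Table 1, Se 0.5 | 0.02 | 0.45 | 0.46 |
| Table 1, Se 0.5 | 0.03 | 0.86 | 0.89 |
| Table 2, Se 0.5 | 0.06 | 0.79 | 0.78 |
| Table 2, Se 0.5 | 0.12 | 0.61 | 0.60 |

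The remaining cells of Table 1 and of the right half of Table 2 are printed as >0.99 and compute as >0.99. The largest gap is 3 points (0.86 against 0.89). It narrows to about 1 point with the exact McNemar test and p01 rounded to 0.005 (0.87). That rounding also explains Table 1's last-row prevalences: 0.12 × 0.2 + 0.005 = 0.029 and 0.12 × 0.5 + 0.005 = 0.065. The right-half prevalences of Table 2 (0.059, 0.064, 0.077, 0.104) match the formula.

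**Step 2: hsRDT prevalence at Se 0.2, Sp 0.95.**

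- p = 0.02: 0.004 + 0.0490 = 0.0530
- p = 0.03: 0.006 + 0.0485 = 0.0545
- p = 0.06: 0.012 + 0.0470 = 0.0590
- p = 0.12: 0.024 + 0.0440 = 0.0680

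To three decimals these are the four numbers printed under power. The numbers printed as prevalence are impossible here: false positives alone contribute at least 0.044 in every row, and the largest printed value is 0.029. Working back from the printed values gives a specificity of 0.994–0.995.

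**Step 3: power at Se 0.2, Sp 0.95.**

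| p | p10 | p01 | Expected discordant pairs (1980·p10 / 1980·p01) | Power, normal | Power, exact | Printed |
|---|---|---|---|---|---|---|
| 0.02 | 0.016 | 0.0490 | 32 / 97 | 0.9999 | 1.000 | 0.053 |
| 0.03 | 0.024 | 0.0485 | 48 / 96 | 0.982 | 0.981 | 0.055 |
| 0.06 | 0.048 | 0.0470 | 95 / 93 | 0.052 | 0.044 | 0.059 |
| 0.12 | 0.096 | 0.0440 | 190 / 87 | 1.000 | 1.000 | 0.068 |

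The 3% row in full: d = 0.0245, s = 0.0725, √1980 = 44.50. Then d√n = 1.090, 1.96√s = 0.528 and √(s − d²) = 0.268, so Φ(0.562/0.268) = Φ(2.10) = 0.982; the other tail is negligible.

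Uncorrected and continuity-corrected chi-square versions, and an unpaired two-proportion calculation, all give at least 0.97 in rows 1, 2 and 4. No choice of method brings those rows near the printed values.

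**Step 4: where the errors cancel.** p10 = p01 when p(1 − Se) = (1 − p) × 0.05. For Se 0.2 this is p = 0.05/0.85 = 5.9%; for Se 0.5 it is 0.05/0.55 = 9.1%.

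**The case against.** The case on the other side accepts the arithmetic and disputes how much it matters.

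- **Nothing else depends on these cells.** The sample size comes from feasibility, both power claims in the text come from Table 1, and the base assumption is specificity 0.995. Section 7.2 will estimate sensitivity and specificity with confidence intervals, so false positives would show in the results. This stands and keeps the point moderate in weight.
- **The misprint does not flatter the study.** Three rows understate power. True, but the high power at 2% and 3% is for hsRDT exceeding PCR, so it is no evidence of good performance either.
- **The 6% entry is nearly right.** Printed 0.059 against about 0.05. This stands: that cell holds the wrong quantity but is not materially wrong in size.
- **The right half already shows over-calling**, for example 0.059 against 0.02. This also stands, but only for sensitivity 0.5; the plan's base case is 0.2.
- **Cancellation near 6% is specific to sensitivity 0.2.** Correct, and the added sentence must say so.
- **The corrected powers assume independent pairs**, although recruitment is by household around index cases. With assumed design effects of 1.5 and 3 (effective n 1320 and 660), the 0.98 would fall to 0.91 and 0.65. The plan's own tables make the same independence assumption, so the replacement values are like for like; clustering is a separate matter.

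Broken PDF extraction is an unlikely explanation. The rows have the expected number of cells, the right half is correct, and extraction would not carry Table 1's values into Table 2.

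**Conclusion.** The left half of Table 2 is wrong as written. Its power column contains the hsRDT prevalences for specificity 0.95, and its prevalence column belongs to specificity 0.995. The pattern is what one would see if a copy of Table 1 had its new values entered one column too far to the right.

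On the plan's own assumptions, the powers should be >0.99, 0.98, 0.05 and >0.99. Those at 2%, 3% and 12% are misstated by more than 90 percentage points. The hsRDT prevalences should be 0.053, 0.055, 0.059 and 0.068, which is 5.9, 5.0, 3.5 and 2.3 times the printed values. The substantive message changes as well: at sensitivity 0.2 power is lost only close to 6% prevalence, where the two kinds of error balance, and not across the whole range.

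The error is confined to these eight cells. It does not change the sample size, Table 1, the planned tests or the right half of Table 2.

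**What to change.** Replace the left half of Table 2 with:

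| Prevalence by usPCR | Sensitivity | Specificity | Estimated prevalence by hsRDT | Power |
|---|---|---|---|---|
| 0.02 | 0.2 | 0.95 | 0.053 | >0.99 |
| 0.03 | 0.2 | 0.95 | 0.055 | 0.98 |
| 0.06 | 0.2 | 0.95 | 0.059 | 0.05 |
| 0.12 | 0.2 | 0.95 | 0.068 | >0.99 |

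Add one sentence below the table, for example: *At specificity 0.95 and usPCR prevalence of 2–3%, the difference detected is an excess of hsRDT positives over PCR; with sensitivity 0.2, false positives and false negatives cancel near 6% prevalence (near 9% with sensitivity 0.5), where this comparison cannot distinguish hsRDT from PCR.* State that the powers assume independent subjects, as in Table 1.

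The cost is eight table cells and a short note. No change to the design, sample size or analysis is needed.

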# 7.2. Analytical Plan

All data will be double-entered into Epi-Info and any discrepancies will be reviewed against the paper forms. All analyses will be conducted using Stata/SE (version 14), using data from the participant interviews and the three parasitological tests.

The malaria test positivity rate will be calculated as a proportion of samples tested that are positive using cRDT, hsRDT and PCR, respectively. Corresponding 95% confidence intervals (CIs) will be computed using exact method. A 2x2 table method will be used to calculate the sensitivity, specificity, positive and negative predictive values of hsRDT (and cRDT) and their corresponding 95% CIs using PCR as gold standard. The malaria prevalence by each test (e.g., the rate of malaria test positive) will be compared between each two tests (hsRDT vs PCR; cRDT vs PCR; hsRDT vs cRDT) using McNemar test. All statistical tests will be performed with a two-sided significance level of 0.05.

Descriptive analysis will be conducted to assess socio-demographics characteristics. Univariate analysis will include t-test and non-parametric methods for continuous variables and chi-square test for comparison of categorical variables. Multi-level regression models will be developed to examine risk factors significantly associated with malaria infections, accounting for clustering by index case.

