# 5. Methodology

# 5.1. Study Design & Overview

This is a prospective community-based single-center reactive case detection (RCD) study to assess the performance of hsRDT versus cRDT in identifying individuals with malaria infection ("Secondary case") in a population living and/or working in a close physical proximity to an "index case."

"Index case" is defined as a malaria infection identified by passive surveillance by local health services (rural health center, sub-centers) or village malaria workers (VMWs), by cRDT or microscopy.

"Secondary case" is defined as any malaria infection identified by any of the study diagnostic test: cRDT, hsRDT or PCR, regardless of the presence of acute clinical illness. The secondary cases will be identified actively and systematically around the residence, or work place if relevant, of the index case.

The study will be initiated after obtaining administrative (Myanmar MoHS, NMCP, PMI) and ethical approval (Myanmar DMR ERC, CDC IRB and UMB IRB) from all relevant institutions. Consent, and assent and adult permission when appropriate, will be sought for all index cases and secondary cases. Only those who are eligible and provide informed consent will be enrolled in the study.

All index cases parasitologically confirmed by cRDT or microscopy will be appropriately and promptly notified to the study team, using mobile phone technology where possible, to ensure timely enrollment. The home of the index case, or work place when relevant, will be visited within three days of the diagnosis, and s/he will be interviewed with a standardized case investigation form. During the visit, all members of the index case household and all members of the nearest 10 households, aged 5 years or above, will be invited to participate in the study. All participants in the study will be interviewed with a structured questionnaire, tested with cRDT and hsRDT, and a dried blood spot (DBS) will be collected for subsequent PCR analysis. All cases parasitologically confirmed by cRDT or hsRDT will be appropriately treated, following the national treatment guideline. DBS samples will be collected, processed and stored until analysis following the World Wide Antimalarial Resistance (WWARN) Molecular Testing for Malaria Standard Operating Procedures DBS Sample Collection and Transportation (http://www.wwarn.org/learning/procedures/dbs-sample-collection-andtransportation).

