# 5.5. Recruitment Procedures, Identification index cases and selection of secondary cases

Suspected malaria cases attending local health services (rural health center and sub-centers) or village malaria workers (VMW) will be tested with a cRDT as in routine practice. All cases parasitologically confirmed by cRDT will be treated according to national guidelines, and asked for informed consent to participate in the study. If the patient gives informed consent, the VMW or basic health staffs will promptly notify the study team, using mobile phone. Additionally, finger prick blood will be collected from the index case to test with hsRDT, and on dry blood spot (DBS) for later PCR analyses.

The study team will conduct the investigation visit at the residence of the index case within 3 days, and the index cases will be interviewed using a standard case investigation form (Annex 1). All members of the index case's household will be invited to participate in the study and

interviewed using the participants' questionnaires (Annex 2) to assess a history of malaria in previous year, travel information, and utilization of malaria prevention measures. The nearest ten households around the index case's household will be identified by using household listing. All members, including temporary visitors, of these ten households will be invited to participate in the study and interviewed using the participants' questionnaires (Annex 2), tested with cRDT and hsRDT, and a DBS will be collected for subsequent analysis. If the index case reports traveling to or working in the forest or other risk areas, co-travelers or co-workers will be also recruited in the study, when feasible.

Study participants who tested positive on cRDT or hsRDT will be treated according to national guidelines, in compliance with WHO recommendations and NMCP policies, which call for treatment of any RDT-positive infection. Although the diagnostic performance of hsRDT is under investigation, there is enough evidence that cRDT fails to detect low density infections, therefore treatment of hsRDT-positive malaria is conservative and ethically justifiable.

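### Clustering around 50 index cases is handled only in the risk-factor models, not in the intervals for positivity and predictive values, the McNemar tests or the power

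*Combined protocol and SAP*

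**What the plan says.** Recruitment is by neighbourhood. Section 5.1 invites "all members of the index case household and all members of the nearest 10 households", and section 5.5 adds that "co-travelers or co-workers will be also recruited in the study, when feasible". Section 7.1 builds the sample size as 4.5 persons x 11 households x 50 index cases x 0.80 = 1,980.

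Section 7.1 defines the main comparison: "The primary endpoint of this proposed study is the prevalence of secondary malaria cases identified by hsRDT in comparison with usPCR prevalence". For 2% prevalence, hsRDT sensitivity 0.2 and specificity 0.995 it states that "a sample size of 1980 subjects achieves at least 92% power to detect the difference in prevalence between hsRDT and usPCR", using an ordinary two-sided McNemar test.

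The analysis methods in section 7.2 are:

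- Positivity rates: "Corresponding 95% confidence intervals (CIs) will be computed using exact method".
- Accuracy measures: "A 2x2 table method will be used to calculate the sensitivity, specificity, positive and negative predictive values of hsRDT (and cRDT"; no interval type is named.
- Test comparisons: positivity by each test "will be compared between each two tests (hsRDT vs PCR; cRDT vs PCR; hsRDT vs cRDT) using McNemar test".
- Risk factors: "Multi-level regression models will be developed to examine risk factors significantly associated with malaria infections, accounting for clustering by index case".

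The last item is the only place where clustering is mentioned.

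**The concern.** Reactive case detection rests on the idea that infections gather around an index case. Section 5.3 reports 2016 test positivity between 0% and 13% across the study villages. That range is not an ICC, but it makes independence hard to defend. The plan itself accepts the correlation for the risk-factor models.

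McNemar's test deals with the pairing of two tests within one person. It does not deal with correlation between people around the same index case. An exact binomial interval likewise assumes independent people.

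Positivity by each test is the outcome of specific objective 1, and PCR prevalence is the reference in the primary comparison. Section 11 says the results will feed into national procedures for active case detection. Intervals that are too narrow would overstate how well prevalence and negative predictive value (NPV) are known, and section 7.1 would promise more power than a valid test has.

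**Working it through.** **Inputs.** From section 7.1: N = 1,980, 50 index cases, two-sided 5% test, the sensitivities (Se), specificities (Sp) and prevalences of Tables 1 and 2. Average cluster size is 1,980 / 50 = 39.6. The ICC is an assumption: 0.01, 0.02 and 0.05. Only infection is clustered; test errors are independent given infection.

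**1. Reproduce the stated 92%.** At prevalence π = 0.02, Se 0.2, Sp 0.995, the discordant cells are:

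- PCR+ / hsRDT−: 0.02 x 0.8 = 0.0160
- PCR− / hsRDT+: 0.98 x 0.005 = 0.0049

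The difference is 0.0111 and the sum 0.0209. The variance of the paired difference is 0.0209 − 0.0111² = 0.02078. Power = Φ[(0.0111 x √1980 − 1.96 x √0.0209) / √0.02078] = Φ(1.46) = 0.928. The exact McNemar test gives 0.923. The printed 0.92 is therefore the figure for 1,980 independent people.

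**2. Design effects.** For PCR prevalence the design effect is 1 + (39.6 − 1) x ICC = 1.39, 1.77 and 2.93. For the paired difference it is smaller, because only part of that difference depends on infection. The ICC is multiplied by [(1 − Se) + (1 − Sp)]² π(1 − π) / variance:

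- 2%, Se 0.2: 0.805² x 0.0196 / 0.02078 = 0.61. Design effect 1.24, 1.47, 2.18.
- 3%, Se 0.5: 0.505² x 0.0291 / 0.01975 = 0.376. Design effect 1.145, 1.29, 1.73.

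**3. Simulation.** Beta-binomial infection, 30 clusters of 40 and 20 of 39, up to 40,000 replicates per cell. The adjusted test uses an Obuchowski-type variance and t with 49 df. Repeat runs agree within about one percentage point.

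Power of the cluster-adjusted test, hsRDT vs PCR:

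| Scenario | Stated | ICC 0 | 0.01 | 0.02 | 0.05 |
|---|---|---|---|---|---|
| Table 1: 2%, Se 0.2 | 92% | 94% | 89% | 85% | 68% |
| Table 1: 2%, Se 0.5 | 45% | 45% | 40% | 36% | 25% |
| Table 1: 3%, Se 0.5 | 86% | 90% | 87% | 83% | 72% |
| Table 2: 6%, Se 0.5 | 79% | 77% | 73% | 69% | 61% |
| Table 2: 12%, Se 0.5 | 61% | 59% | 54% | 49% | 39% |

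Largely unaffected: Table 1 at 3%, Se 0.2 (99.8 / 99.6 / 97.6%), Table 1 at 6% and 12% (above 99.9%), and Table 2 with Se 0.5 at 2% and 3% (at least 99.8%).

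Coverage of a nominal 95% exact interval (for predictive values, exact is assumed because the plan names no type):

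| Quantity | ICC 0.01 | 0.02 | 0.05 |
|---|---|---|---|
| PCR prevalence, 2% | 91% | 87% | 76% |
| PCR prevalence, 3% | 92% | 87% | 77% |
| NPV, 2%, Se 0.2, Sp 0.995 | 93% | 90% | 81% |
| NPV, 3%, Se 0.5, Sp 0.995 | 94% | 92% | 86% |
| PPV, 6%, Se 0.5, Sp 0.95 | 95% | 93% | 89% |

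Positive predictive value (PPV) at Sp 0.995 keeps 94–97%. Sensitivity and specificity keep 95–97% in every cell. Logit-scale cluster-robust intervals restore 94–95% for PCR prevalence and NPV, and 94–96% for PPV.

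**4. False rejection by plain McNemar.** This needs nearly equal prevalences. At 6%, Se 0.2, Sp 0.95, hsRDT prevalence is 0.2 x 0.06 + 0.05 x 0.94 = 0.059 against 0.060. Plain McNemar then rejects in about 7%, 9% and 14–15% of runs; the adjusted test rejects in about 5%. For hsRDT vs cRDT with equal accuracy, plain McNemar rejects in 4.8–5.3%, so there is no inflation.

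**The case against.** Several counter-arguments have force.

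- The ICC is not in the documents, and the striking figures need 0.05. At 0.01 the 92% falls only to 89% and the 86% claim still holds. This stands: the omission is plain from the text, but its size is conditional.
- The interval for hsRDT positivity, the test of interest, is hardly touched at Se 0.2: coverage is 94–96%. This also stands. At Se 0.5 and ICC 0.05, however, it falls to about 91% (2%) and 88% (3%).
- Over-rejection appears only where false positives offset missed infections, and no Table 1 scenario is like that. This is correct, so the Type I error problem is narrow.
- In Table 2, two points of each shortfall exist at ICC 0 and come from the t-based test (77% against 79%, 59% against 61%). This is correct; the rest is clustering.
- Section 3.1 gives hsRDT vs cRDT as the main goal, and objective 2 concerns sensitivity and specificity. Clustered infection alone harms neither the test at equal accuracy nor those intervals.

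None of this rescues the intervals for PCR prevalence and NPV, which are too narrow at every ICC examined. A clustered test for hsRDT vs cRDT does little harm and keeps the three comparisons consistent.

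**Conclusion.** The concern holds. The plan recognises clustering by index case and then leaves it out of the positivity and predictive-value intervals, the McNemar tests and the power calculation.

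The firm consequence is under-coverage for PCR prevalence and NPV. PPV is affected when specificity is 0.95. Power is overstated in Table 1 at 2% (both sensitivities), at 3% with Se 0.5 once the ICC reaches 0.02, and in Table 2 with Se 0.5 at 6% and 12%. Sensitivity and specificity intervals would be too narrow only if test errors themselves cluster, which is not claimed here.

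The sizes rest on an assumed ICC of 0.01 to 0.05, beta-binomial infection and independent test errors. This should be fixed before analysis; it does not undermine the design.

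**What to change.** In section 7.2:

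- Compute intervals for positivity rates, PPV and NPV with variance robust to index-case clustering on the logit scale, or by cluster bootstrap. Use the exact interval if a numerator is 0 or equals its denominator.
- Replace plain McNemar with a clustered version (GEE, Durkalski or Obuchowski) for all three test pairs.
- Name exact intervals for sensitivity and specificity; a cluster-robust version there is optional.
- Assign each person, including co-workers and co-travellers, to one index-case cluster, and count each person once where neighbourhoods overlap.

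In section 7.1, restate power over a stated ICC range, keeping N at 1,980.

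A separate correction is needed in Table 2. The four power entries at Se 0.2 (0.053, 0.055, 0.059, 0.068) equal 0.2 x prevalence + 0.05 x (1 − prevalence) = 0.053, 0.0545, 0.059, 0.068. They are hsRDT prevalences, not power.

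The cost is some SAP wording and a few lines of code; the multi-level model already needs the index-case identifier. Intervals become wider at ICC 0.01 / 0.02 / 0.05. The median width for PCR prevalence at 2% goes from 1.3 to 1.5 / 1.7 / 2.1 percentage points, and for NPV at 2%, Se 0.2, from 1.2 to 1.3 / 1.5 / 1.8. Stated power falls in the marginal scenarios.
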